14.7. Appendix 7: Reporting Standards for Missing Data**14.7.1. Premature Withdrawals**

Element	Reporting Detail
General	
 • The protocol objective is to collect data over the full study treatment period (up to Week 52) for all participants, whether they continue on interventional product (IP) and complete Week 52 on-treatment, or whether they withdraw prematurely from IP. 
 ○ For the participants who withdraw prematurely from IP before Week 52 and agree to the continued collection of data off-treatment, data will be collected for up to 52 weeks after randomization (or up to 76 weeks if the participant enters the Follow-up period after Week 52) either through clinic visits or via phone contact, in accordance with the participants existing visit schedule. ○ Where available, off-treatment data will be included in the analysis of the co-primary endpoints and, unless otherwise indicated, in the analysis of other efficacy endpoints. • A participant will be considered to have completed study treatment if he/she continues to take study treatment until Visit 14 (Week 48) and completes Visit 15 (week 52). • As specified in the protocol participants will be considered to have completed the study upon completion of Visit 15 (Week 52) regardless of whether they continue to take IP. • A participant eligible for the no-treatment follow-up will be considered to have completed follow-up if they continue to participate in the study until Visit 18 (Week 76) • All available data from participants who were withdrawn from the study will be listed and all available planned data will be included in summary tables and figures, unless otherwise specified. • Withdrawal visits will be slotted as per Appendix 3: Assessment Windows or will be summarised as withdrawal visits.
Pre-Screen/Screen and Run-in Failures	
 • Participants are assigned a subject number at the time of signing informed consent. • Pre-Screen Failure: A participant who is assigned a subject number but did not continue through to Visit 1. • Screening Failure: Participant performs a Visit 1 procedure, but does not enter the run-in period • Run-in Failure: Participant enters the run-in period, may perform a Visit 2 procedure, but is not subsequently randomised.

14.7.2. Handling of Missing Data

Element	Reporting Detail
General	
 • Missing data occurs when any requested data is not provided, leading to blank fields on the collection instrument: 
 ○ These data will be indicated using a “blank” in data listings. Where all data for a specific visit are missing the visit will be excluded from the listing. ○ Answers such as “Not applicable” and “Not evaluable” are not considered to be missing data and should be displayed. 
Values reported as 'BLQ' are not considered as missing data and are handled as detailed in

CONFIDENTIAL

205687

Element	Reporting Detail
	Section 14.6.6, these values will be displayed in the listings and included in any summary/analysis outputs.
Outliers	
 All data will be included in the summaries and analyses of each endpoint. The exclusion of participants or participant data from any supplementary analyses will be documented within footnotes and where required the clinical study report.
Covariate information	
 Participants with missing information for a covariate included in the analysis model will be excluded from the analysis.

14.7.2.1. Handling of Missing Dates

Element	Reporting Detail
General	
Start or end dates which are completely missing (i.e. no day, month or year is specified) will remain missing, with no imputation applied.
 
Derivations requiring this information such as time to onset and duration will be set to missing.

14.7.2.2. Handling of Partial Dates

Element	Reporting Detail
General	
 Partial dates will be displayed as captured in subject listings.
Adverse Events	
 The eCRF allows for the possibility of partial dates to be recorded for AE start and end dates. For partial dates the following imputations will be applied: 
 Partial Start Date: '01' will be used for a missing day and 'Jan' will be used for a missing month. If this results in a date prior to the start of study treatment, then the treatment start date will be used. The event will then be considered 'On-treatment' as per Section 14.4.1.3. Partial Stop Date: '28/29/30/31' will be used for a missing day (dependent on the month and year) and 'Dec' will be used for a missing month. If this results in a date after the study stop date, then the study stop date will be used. The above imputations will be applied when calculating the time to onset and duration of the event.
Concomitant Medications	
 For concomitant medications partial dates will be imputed as follows: 
 Partial start date: '01' will be used for a missing day and 'Jan' will be used for a missing month Partial stop date: '28/29/30/31' will be used for a missing day (dependent on the month and year) and 'Dec' will be used for a missing month.

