### 9.3.1. Time Period and Frequency for Collecting AE and SAE Information

- All SAEs will be collected from the signing of the ICF until the end of the study at the time points specified in the SoA (Section 2).

- All AEs will be collected from the start of treatment until [the end of the study at the time points specified in the SoA (Section 2)].
- Medical occurrences that begin before the start of study treatment but after obtaining informed consent will be recorded on the Medical History/Current Medical Conditions section of the CRF not the AE section.
- All SAEs will be recorded and reported to the sponsor or designee within 24 hours, as indicated in [Appendix 4](#). The investigator will submit any updated SAE data to the sponsor within 24 hours of it being available.
- Investigators are not obligated to actively seek AEs or SAEs in former study participants. However, if the investigator learns of any SAE, including a death, at any time after a participant has been discharged from the study, and he/she considers the event to be reasonably related to the study treatment or study participation, the investigator must promptly notify the sponsor.
- The method of recording, evaluating, and assessing causality of AEs and SAEs and the procedures for completing and transmitting SAE reports are provided in [Appendix 4](#).

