14.4.1.3. Phases for Adverse Events

Study Phase	Definition
Pre-Treatment	Event Start Date < Interventional Product Start Date
On-Treatment	Interventional Product Start Date \leq Event Start Date \leq Interventional Product Stop

CONFIDENTIAL

2020N427698_00

205687

Study Phase	Definition
	Date + 28 days
Post -Treatment	Participants who do not enter the follow-up period after Week 52: Event Start Date > Interventional Product Stop Date + 28 days Participants who enter the follow-up period after Week 52: Interventional Product Stop Date + 28 days < Event Date ≤ Week 52 Visit Date
Post -Treatment (Follow-up after Week 52)	Participants who enter the follow-up period after Week 52: Week 52 Visit Date < Event Date

NOTES: An event will be considered On-treatment if the event start date is missing and/or the interventional product stop date is missing

Where time of event is recorded, the time of event and time of first dose will be considered to differentiate between Pre-treatment and On-treatment events.

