14.7.2.2. Handling of Partial Dates

Element	Reporting Detail
General	
 Partial dates will be displayed as captured in subject listings.
Adverse Events	
 The eCRF allows for the possibility of partial dates to be recorded for AE start and end dates. For partial dates the following imputations will be applied: 
 Partial Start Date: '01' will be used for a missing day and 'Jan' will be used for a missing month. If this results in a date prior to the start of study treatment, then the treatment start date will be used. The event will then be considered 'On-treatment' as per Section 14.4.1.3. Partial Stop Date: '28/29/30/31' will be used for a missing day (dependent on the month and year) and 'Dec' will be used for a missing month. If this results in a date after the study stop date, then the study stop date will be used. The above imputations will be applied when calculating the time to onset and duration of the event.
Concomitant Medications	
 For concomitant medications partial dates will be imputed as follows: 
 Partial start date: '01' will be used for a missing day and 'Jan' will be used for a missing month Partial stop date: '28/29/30/31' will be used for a missing day (dependent on the month and year) and 'Dec' will be used for a missing month.

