3.13.	Safety	AE1	Summary of Adverse Events Leading to Withdrawal from Study by System Organ Class	IDSL; Footnote: Includes data reported up to Week 52	SAC [2]

CONFIDENTIAL

205687

Safety: Tables					
No.	Population	IDSL / Example Shell	Title	Programming Notes	Deliverable [Priority]
3.14.	Safety	AE1	Summary of Adverse Events Reported on Day of Dosing by System Organ Class	Footnote: Includes data reported up to Week 52	SAC [2]
Serious and Other Significant Adverse Events					
3.15.	Safety	AE3	Summary of Fatal Serious Adverse Events		SAC [1]
3.16.	Safety	AE3	Summary of Fatal Drug-Related Serious Adverse Events		SAC [2]
3.17.	Safety	AE1	Summary of Non-Fatal Serious Adverse Events by System Organ Class	Include on-treatment and post-treatment	SAC [2]
3.18.	Safety	AE1	Summary of Non-Fatal Serious On-Treatment Adverse Events by System Organ Class		SAC [1]
3.19.	Safety	AE1	Summary of Non-Fatal Serious Post-Treatment Adverse Events by System Organ Class	Footnote: Includes data reported up to Week 52	SAC [2]
3.20.	Safety	AE1	Summary of Serious Adverse Events by System Organ Class	Include on-treatment and post-treatment	SAC [1]
3.21.	Safety	AE1	Summary of Serious On-Treatment Adverse Events by System Organ Class		SAC [2]
3.22.	Safety	AE1	Summary of Serious Post-Treatment Adverse Events by System Organ Class	Footnote: Includes data reported up to Week 52	SAC [2]
3.23.	FU	AE1	Summary of Serious Adverse Events Reported During the Follow-Up Period After Week 52 by System Organ Class		SAC [2]
3.24.	Safety	AE1	Summary of Serious Drug-Related On-Treatment Adverse Events by System Organ Class		SAC [2]
3.25.	Safety	AE1	Summary of Pre-Treatment Serious Adverse Events by System Organ Class		SAC [2]
3.26.	Safety	AE16	Summary of Serious Adverse Events by System Organ Class and Preferred Term (Number of Subjects and Occurrences)	FDAAA, EudraCT	SAC [2]

CONFIDENTIAL

205687

Safety: Tables					
No.	Population	IDSL / Example Shell	Title	Programming Notes	Deliverable [Priority]
3.27.	Safety	SHELL	Summary of Deaths	Includes all deaths separating those reported in no-treatment follow-up	SAC [2]
Adverse Events of Special Interest					
3.28.	Safety	SHELL	Summary of On-Treatment Serious AEs and AEs of Special Interest: Incidence, Relative Risk and Risk Difference (Placebo vs 100mg SC)		SAC [2]
3.29.	Safety	AE1	Summary of On-Treatment Adverse Events of Special Interest: Systemic Reactions Reported by the Investigator as Meeting the Criteria for Anaphylaxis		SAC [2]

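### A partial SAE start date that is known to lie before first dose is still moved to the first-dose date and counted as on-treatment

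*SAP*

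**What the plan says.** The rule is in the current SAP (RAP Amendment 1), section 14.7.2.2, under Adverse Events. The superseded RAP in the same file has the same sentence.

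- Partial dates are an accepted input: "The eCRF allows for the possibility of partial dates to be recorded for AE start and end dates".
- Completion: "Partial Start Date: '01' will be used for a missing day and 'Jan' will be used for a missing month".
- Override: "If this results in a date prior to the start of study treatment, then the treatment start date will be used".
- Phase: "The event will then be considered 'On-treatment' as per Section 14.4.1.3".
- The completed dates also feed time to onset and duration.

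Section 14.4.1.3 defines a pre-treatment event as "Event Start Date < Interventional Product Start Date". The list of safety tables in 14.12.8 plans a display for such events, Table 3.25: "Summary of Pre-Treatment Serious Adverse Events by System Organ Class".

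Protocol 9.3.1 sets the collection windows. For serious events: "All SAEs will be collected from the signing of the ICF until the end of the study". For adverse events in general the window opens later: "All AEs will be collected from the start of treatment until" the end of the study. Anything that begins between consent and first dose otherwise goes to medical history.

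**The concern.** Moving a start date up to first dose is a sensible convention when the recorded part of the date leaves the order of event and dose open. That is so when the month is the first-dose month, or when only the year is known and it is the first-dose year. As written, the override goes further. It applies to every partial date that completes to before first dose, including dates whose recorded month or year already proves that the event came first. It also ignores a stop date that proves the same thing.

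In those cases the rule replaces a known fact with a wrong one. An event that began, and perhaps ended, before any study drug would count as on-treatment. The table meant for pre-treatment SAEs would be short by the same event.

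**Working it through.** The plan states no figure that depends on this rule, so there is none to reproduce. The check follows the rule on one example and then sizes it.

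**Example (assumed dates).** First dose is 20 May. The SAE start is recorded only as April of that year, and its stop date is 30 April. The formulas are in SAP 14.6.6: duration = end − start + 1. Time since first dose = start − first dose, plus 1 when the start is on or after first dose.

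| Step | Rule as written | Override limited to compatible dates |
|---|---|---|
| Completed start | 1 April | 1 April |
| Start used | 20 May | 1 April |
| Phase (14.4.1.3) | On-treatment | Pre-treatment |
| Time since first dose | 0 + 1 = Day 1 | −49 days |
| Duration | −20 + 1 = −19 days | 29 + 1 = 30 days |

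The negative duration shows that the specification fails on input that the eCRF permits.

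**Comparison within the plan.** The concomitant medication rule in the same section uses the same 01/January completion but has no override. A drug started in April for this SAE would be pre-treatment under 14.4.1.4, while the SAE itself is on-treatment.

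**How often the month alone settles the order.** Take run-in onset days as evenly spread, first-dose dates as spread over the year, and only the day as missing. An onset k days before first dose falls in an earlier month when the first-dose day of the month is at most k. For k up to 28 that is 12k of 365 dates.

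- 28-day run-in (the nominal 4 weeks): the average over k = 1 to 28 is 12 × 14.5 / 365 = 0.477, about 48%.
- 42-day run-in (the 6-week limit in Protocol 6.3, criterion 10): the sum over k = 1 to 28 is 12 × 406 = 4,872. Add 347 for k = 29, 358 for k = 30 and 12 × 365 = 4,380 for k = 31 to 42. The total is 9,957 / (42 × 365) = 0.650, about 65%.

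Under the rule as written, none of these events is classed as pre-treatment.

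**Expected number moved wrongly.** The documents give neither the number of pre-dose SAEs nor the share with partial dates. Assume 2 to 6 in 400 participants and 5 to 10%.

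- Low: 2 × 0.05 × 0.48 = 0.05 events.
- High: 6 × 0.10 × 0.65 = 0.39, about 0.4 events.

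This range omits same-month events whose stop date precedes first dose, which are also misplaced. Adding them cannot take it past all partially dated pre-dose SAEs: 2 × 0.05 = 0.1 to 6 × 0.10 = 0.6. That wider range also includes same-month events for which the override is reasonable.

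**The case against.** The strongest reply is that the rule suits nearly all the data it will meet. Non-serious events are collected only from first dose, so a completed date before dosing is usually an artefact of the 01/January convention, and correcting it is sensible. It also fits 14.4.1.3, which treats an event with a missing start date as on-treatment.

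Partial dates should also be rare for SAEs. They are reported within 24 hours, and the data are cleaned before database freeze. Protocol 9.1.1 limits SAE reporting from pre-screening to events related to study participation, and the schedule places the first SAE review at Visit 1, so the time before screening adds little. Participants who fail run-in never enter the Safety population. Listings show partial dates as captured, so a reader could spot a misplaced event.

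All of this stands as a limit on size. It does not correct the rule: a listing does not repair a table count, and a convention for uncertain order does not justify overriding a known order.

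Three stronger readings are tempting, and the documents do not support them:

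- **Safety bias against mepolizumab.** Run-in events precede randomisation and the rule is identical in both arms, so any moved event adds noise or slight dilution to the relative risk, with no expected direction.
- **A visible rise in an arm's SAE total.** That needs one whole event to be moved in one arm. The expected number is well under one for the trial, and no document shows that such an event exists.
- **Extra events in the day-of-dosing display.** That display needs an onset time at or after dosing, so these events need not appear there.

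**Conclusion.** The point holds as a narrow wording defect in current SAP 14.7.2.2. The override assigns the wrong phase to a partially dated SAE whose recorded month or year, or recorded stop date, places it before first dose. It conflicts with the plan's own pre-treatment definition and takes such events out of Table 3.25. In practice only SAEs from the pre-dose period are affected. Fully dated SAEs are classified correctly.

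The expected size is about 0.05 to 0.4 events across the trial. That rests on assumed numbers of pre-dose SAEs and partial dates, and on onset days spread evenly over the run-in. No efficacy endpoint or hypothesis test uses the rule. It is a minor clean-up, worth making because it costs almost nothing.

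**What to change.** In 14.7.2.2, restrict the override. When the completed start date falls before first dose, use the treatment start date only if both conditions hold:

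1. the known part of the start date (month and year, or the year alone) equals that of first dose; and
2. no recorded stop date precedes first dose.

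Otherwise keep the 01/January completed date and let 14.4.1.3 class the event as pre-treatment. Attach the sentence that makes the event on-treatment to the first case only.

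Dates whose order is unclear remain on-treatment, so no caution is lost. The cost is one sentence in the SAP and one condition in the program. No protocol or data collection change is needed.

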14.7.2.3. Missing Data for Statistical Analysis

Element	Reporting Detail
General	

• The study is designed to collect data for the 52 weeks following randomisation for all participants, including for participants who prematurely withdraw from interventional product. The following scenarios may arise.

1) Participant completes interventional product and study
2) Participant prematurely withdrawn from interventional product and agrees to continued data collection off-treatment for 52 weeks following randomisation
3) Participant prematurely withdrawn from interventional product and initially agrees to continued off-treatment data collection, but subsequently withdraws from the study prior to 52 weeks following randomisation
4) Participant prematurely withdrawn from interventional product and does not agree to continued off-treatment data collection
• For participants under any scenario missing data may arise intermittently due to nonattendance at scheduled visits. For participants under scenarios 3 and 4 missing data will arise due to premature withdrawal from the study.
• Unless otherwise specified on-treatment data and where available off-treatment data will be included in the analysis of efficacy endpoints.

CONFIDENTIAL

205687

14.8. Appendix 8: Values of Potential Clinical Importance**14.8.1. Laboratory Values of Potential Clinical Concern**

Haematology				
Laboratory Parameter	Units	Age Category (years)	Clinical Concern Range	
			Low Flag (< x)	High Flag (>x)
Hematocrit	Ratio of 1	12+	0.201	0.599
Haemoglobin	G/L	12+	71	199
Platelet Count	GI/L	1+	31	1499
While Blood Cell Count (WBC)	GI/L	12+	1.1	

Clinical Chemistry				
Laboratory Parameter	Units	Age Category (years)	Clinical Concern Range	
			Low Flag (< x)	High Flag (>x)
ALT	U/L	3-12		>143 (and Total Bilirubin >43)
	U/L	13+		>239 (and Total Bilirubin >43)
Calcium	mmol/L	3+	1.50	3.24
Creatinine Phosphokinase	IU/L	12+		>5 x ULN
Glucose	mmol/L	1+	2.2	27.8
Phosphorus, Inorg	mmol/L	3+	0.32	
Potassium	mmol/L	3+	2.8	6.5
Sodium	mmol/L	0+	120	160

Possible Hy's Law Cases				
Test Analyte	Units	Category	Clinical Concern Range	
ALT, Bilirubin			ALT ≥ 3xULN and Bilirubin ≥ 2xULN (>35% direct)	
ALT, INR			ALT ≥ 3xULN and INR > 1.5	

NOTES: ULN=Upper Limit of Normal

CONFIDENTIAL

205687

14.9. Appendix 9: Population Pharmacokinetic (PopPK) Analyses

14.9.1. Population Pharmacokinetic (PopPK) Dataset Specification

Specifications for the generation of the dataset will be provided in a separate document.

14.9.2. Population Pharmacokinetic (PopPK) Methodology

Mepolizumab plasma concentration-time data (samples collected at Weeks 4, 52 and 68; at the Early Withdrawal Visit and the additional follow-up visits (if applicable)) will be analysed by population methods using nonlinear mixed-effects modelling. The analysis will be carried out using appropriate software (e.g., NONMEM or SAS).

14.9.2.1. Base Model

In consideration of the sparse sampling (3 samples post-start of treatment over 68 weeks: Week 4, 52 and 68) and the wealth of mepolizumab PK knowledge, the most recent population PK model will be applied directly to the dataset without estimation (e.g. $\text{maxevals}=0$ in NONMEM) and predictions generated, against which the model will be validated prospectively using appropriate goodness of fit tests. For example, the Anderson-Darling and Cramér–von Mises tests are accepted methods of comparing Empirical Distribution Functions for model and data (i.e. PK concentrations) to evaluate whether independent observations (i.e. observed PK concentrations from the study) are adequately described by a model (i.e. most recent population PK model).

The following will be obtained:

- A description of the key models tested during the model development will be provided and tabulated;
- Population mepolizumab plasma PK parameter estimates with 95% CI from the final model will be tabulated. Goodness of fit plots for the final model will be presented;
- Individual post-hoc PK parameter estimates (such as area under the plasma concentration-time curve over the dosing interval $[AUC (0-\tau)]$, $C_{AV} [AUC (0-\tau)/\tau]$) will be summarised descriptively and listed;
- Individual post-hoc predicted plasma concentrations will be summarised descriptively and listed;
- Accumulation ratio estimate will be assessed at Week 52.

The most recent model consists of a two-compartment pharmacokinetic model with first-order absorption and elimination. Bodyweight is incorporated into the model using allometry with fixed physiological allometric exponents of 0.75 and unity for clearance and volumes, respectively. Albumin and creatinine clearance are also included as covariates of mepolizumab clearance on physiological grounds, however their effects are small and not of clinical relevance. Details of the model can be found in report GlaxoSmithKline Document Number [2015N238436_00](#).

CONFIDENTIAL

205687

14.9.2.2. Investigation of Covariates

The impact of the following prospectively selected covariates on mepolizumab exposure (e.g. clearance) will be evaluated using the procedures described in Section 14.9.2.3.

Category	Covariates
Demographics	Weight (included in the structural model), age, race, gender, country
Baseline clinical status	Creatinine clearance, albumin (both already included in the current model), serum creatinine, alanine aminotransferase, aspartate aminotransferase, alkaline phosphatase, bilirubin, total protein
Baseline disease status	Total endoscopic NP score (centrally read), blood eosinophils and baseline OCS dose
Concomitant medications	If data permits*, e.g. immunosuppressant therapies (e.g. methotrexate, azathioprine and mycophenolate mofetil), proton pump inhibitors, statins, pain relief (e.g. paracetamol, NSAIDs), interferon alfa and antihypertensive drugs
Others	Presence/absence of anti-drug antibodies and previous biologics use (monoclonal antibodies).

*Attempt to investigate those classes of drug will be made providing data permits.

Covariate selection will be based on physiological plausibility, supported by graphical evaluation (PK parameters vs. covariates), and formally by automated linear model fitting using proc glmselect in SAS 9.4 (or higher). Individual PK parameters and covariates will be log-transformed and standardized before analysis. For forward and backward selections, significance levels of 0.1 and 0.05 will be applied respectively, in line with criteria used in previous analyses. Co-linearity between covariates will be carefully considered.

Identified covariates will then be subjected to traditional covariate analysis (with estimation step) and will follow the procedures described in Section 14.9.2.3. If deemed appropriate box plots of systemic clearance versus covariates of interest (e.g. immunogenicity status) will be provided.

